9.11 Visit Requirements

Visit requirements are outlined in Section 2 – Schedule of Activities (SoA). Specific procedure-related details are provided above in Section 9 – Study Assessments and Procedures.

9.11.1 Screening

Within 45 days prior to treatment allocation, potential participants will be evaluated to determine that they fulfill the entry requirements as set forth in Section 6 – Study Population.

The investigator will discuss with each potential participant the nature of the study, its requirements, and its restrictions. Verification should be obtained to confirm the participant's cirrhosis status; the participant's fibrosis score must be reported to support secondary data analysis.

Screening procedures may be repeated after consultation with the Sponsor.

Rescreening

Participants who have previously completed the screening visit (Visit 1) and were deemed eligible for allocation into this study, but failed to be allocated within the 45-day window, may be rescreened to re-evaluate study eligibility. To reconfirm the participant's eligibility, all pre-study evaluations should be repeated, after approval from the Sponsor, except for the following:

- HCV GT determination
- HCV Viral Resistance/RAS

- Hepatitis B virus screening
- HIV serology
- Liver biopsy/FibroScan®
- Liver imaging
- 12-lead ECG

If any of the laboratory or ECG exclusion criteria are met, the site may have the abnormal value retested one time.

9.11.2 Treatment Period

Drug Dispense

Sites should dispense open-label containers of EBR/GZR FDC tablets (2 open-label containers at Day 1 and 1 container at each subsequent dispensing visit) or EBR and GZR pediatric formulation packets at each dispensing visit per the SoA.

An unscheduled visit must occur to get additional medication if the participant will run out of study medication prior to the next scheduled visit.

Dosing

Administration of study medication will be witnessed by the investigator and/or study staff at the first treatment visit and recorded on the participant's SMD. Participants should complete study therapy as defined by the treatment regimen and per Section 7 – Treatments. If dosing is missed or interrupted, the assigned study therapy regimen should still be completed as per Section 7.6 – Treatment Compliance. Additional instructions related to drug administration on PK visit days is provided in Section 9.6.1 – Blood Collection for Plasma EBR/GZR.

Study Medication and Meal Diary

The investigator/study coordinator will give the participant/legally acceptable representative an SMD to be completed during the treatment period of the study. The investigator/study coordinator will be responsible for entering the participant's identification (allocation number), visit number, and the dates before giving the SMD to the participant/legally acceptable representative. The participant/legally acceptable representative will be instructed to record dates/times and the number of tablets/packets of study medication dosed in the SMD for the entire treatment period as well as soft food information (participants on EBR/GZR pediatric formulation only) and meal data as described in Section 9.6.1 – Blood Collection for Plasma EBR/GZR. Only the participant/legally acceptable representative should enter information into the SMD. The participant/legally acceptable representative is to return the completed SMD at each scheduled visit. At all visits during the treatment period, site personnel must verify the accuracy of the dosing SMD by comparing entries with amounts of unused study medication. If a discrepancy is noted, investigator/study coordinator must discuss the discrepancy with the participant/legally acceptable representative, and the explanation must be documented. Only the participant/legally acceptable representative shall make any changes to the entries on the SMD. The

investigator/study coordinator will be responsible for transferring the appropriate information from the SMD onto the appropriate case report form (CRF).

Contraception Confirmation

Throughout the treatment period precaution must be taken to avoid pregnancy in WOCBP. Confirmation must be obtained and documented by site personnel that WOCBP are using acceptable methods of contraception (see Appendix 5). This assessment must be documented in the participant's study chart at each specified visit.

9.11.3 Follow-Up Period

At the completion of study therapy, participants will be seen for follow-up visits at 4, 12, and 24 weeks after the last dose of study medication. Follow-up visits at 8, 16, and 20 weeks after the last dose of study medication will be completed by telephone contact, at which time, site personnel will confirm the participant is doing well and provide a reminder for the FW24 visit.

9.11.4 Discontinued Participants Continuing to be Monitored in the Study

Discontinuation during Treatment Period

Participants who discontinue therapy prior to the last scheduled treatment visit should complete an Early Discontinuation visit and then continue into follow-up visits.

During the Early Discontinuation visit, every effort should be made to:

- Perform all procedures and evaluations per the SoA
- Retrieve all study medication(s) from the participant
- Schedule follow-up contact(s) (telephone or site visit) as appropriate
- Collect the following information, at a minimum:
 - Reason the participant discontinued
 - Date of the last dose of study medication
 - Date of the last assessment and/or contact.
 - All AEs.

Discontinuation for Virologic Failure

Participants who discontinue because they have met criteria for virologic failure (Section 5.4.2.1.1 – HCV RNA Measurements and Endpoint Definitions) while on study therapy should complete an Early Discontinuation visit as outlined in the SoA (Section 2), and will be seen for follow-up visits at 4, 12, and 24 weeks following confirmation of virologic failure.

Participants who meet the virologic failure criterion for relapse (HCV RNA \geq LLOQ following the end of all study therapy, after becoming TND at the end of treatment) will be seen for the remainder of their follow-up visits (eg, 4, 12, and 24 weeks) as outlined in the SoA (Section 2).

Participants who have met virologic failure criteria and are identified as having a treatment-emergent RAS, will be offered follow-up in a 3-year long-term follow-up protocol, MK-5172-017, to determine the persistence of RASs and to determine time course of reversion to wild-type.

Discontinuation during Follow-up Period(s)

Participants who discontinue during the follow-up period (eg, FW4 through FW24) for reasons other than virologic failure should complete an Early Discontinuation Visit as outlined in the SoA (Section 2).

At a minimum, the following information should be collected:

- The reason the participant discontinued.
- The date of the last assessment and/or contact. A follow-up contact (telephone or visit) will be arranged as appropriate.
- SAEs (per reporting requirements outlined in Section 9.3 – Adverse Events, Serious Adverse Events and Other Reportable Safety).

10. Statistical Analysis Plan

This section outlines the statistical analysis strategy and procedures for the trial. Changes to analyses made after the protocol has been finalized will be documented in a supplemental Statistical Analysis Plan (sSAP) and referenced in the CSR for the trial. Post hoc exploratory analyses will be clearly identified in the CSR.

10.1 Statistical Analysis Plan Summary

Key elements of the Statistical Analysis Plan (SAP) are summarized below; the comprehensive plan is provided in Sections 10.2 to 10.12.

Study Design Overview	A Phase IIb Study to Assess the Pharmacokinetics, Safety, and Efficacy of the Combination Regimen of Elbasvir (EBR)/Grazoprevir (GZR) in Pediatric Participants Aged 3 to Less Than 18 Years with Chronic Hepatitis C Infection
Treatment Assignment	This will be an open-label, non-randomized trial. Participants infected with HCV GT1a without baseline NS5A RASs at position 28, 30, 31, and/or 93; GT1b/1-other; or GT4 with HCV RNA <800,000 IU/mL; TN or PR TE (GT1 only); cirrhotic or NC, will be treated with EBR/GZR for 12 weeks within Age Cohorts (12 to <18 years, 7 to <12 years, and 3 to <7 years). Approximately 22 participants in the oldest cohort (12 to <18 years) will be enrolled. Approximately 34 participants will be enrolled in the two younger cohorts, with 12 to 22 participants in each. The total number of participants enrolled in the three cohorts will be ~56.
Analysis Populations	PK: Per-Protocol (PP) Safety: All Participants as Treated (APaT) Efficacy: Full Analysis Set (FAS) and modified FAS (mFAS)
Primary Endpoints	AUC ₀₋₂₄ , C _{max} , C _{trough} , and CL/F of EBR and GZR.
Secondary Endpoints	1. Number of participants experiencing AEs and discontinuing study drug due to AEs. 2. SVR ₁₂ (Sustained Virologic Response 12 weeks after the end of all study therapy), defined as HCV RNA <LLOQ (either TD[u] or TND) 12 weeks after the end of all study therapy.
Statistical Methods for Key Pharmacokinetic and Efficacy Analyses	Geometric means and 95% confidence intervals (CIs) will be provided for AUC ₀₋₂₄ , C _{max} , and CL/F of EBR and GZR by age cohort and dose level. The proportion of participants achieving SVR ₁₂ will be estimated using a 95% CI (via the Clopper-Pearson method). The missing data approach will be Missing=Failure (M=F).
Statistical Methods for Key Safety Analyses	Safety and tolerability will be assessed by clinical review of all relevant parameters including AEs and laboratory tests. Descriptive statistics will be provided for these safety parameters.
Interim Analyses	Periodic safety analyses will be conducted for the accruing data and will be reviewed by an eDMC at regular intervals as outlined in the eDMC charter. This will supplement routine in house medical monitoring.
Multiplicity	No multiplicity adjustment is planned in this Phase IIb study.
Sample Size and Power	With 22 participants in a particular age cohort, it is ~80% likely that the lower and upper bounds of the 95% CI for EBR and GZR AUC ₀₋₂₄ will lie within 44% of the observed GM.

10.2 Responsibility for Analyses/In-House Blinding

The statistical analysis of the data obtained from this trial will be the responsibility of the Clinical Biostatistics department of the Sponsor. The statistical analyses of the PK data will be conducted in collaboration with the Quantitative Pharmacology and Pharmacometrics and Clinical Research departments of the Sponsor.

This trial is being conducted as a non-randomized, open-label study. The Clinical Biostatistics department will generate the allocation schedule for study treatment assignment. Allocation numbers will be assigned via an IVRS/IWRS. Planned interim analyses for ongoing safety monitoring are described in Section 10.7. Study enrollment is likely to be ongoing at the time of any interim analyses. The results of interim analyses will not be shared with the investigators prior to the completion of the trial. The eDMC will serve as the primary reviewer of the results of these analyses and will make recommendations for discontinuation of the trial or protocol modifications to an executive committee of the Sponsor.

An internal statistician not otherwise connected with the trial will conduct analyses and present results to the eDMC. This statistician will not be involved in any discussions regarding modifications to the protocol, statistical methods, identification of protocol deviations, or data validation efforts after the interim analyses. Additional logistical details will be provided in the eDMC Charter. Key aspects of the interim analyses are described in Section 10.7.

10.3 Hypotheses/Estimation

There are no hypotheses to be tested in this trial. Objectives of the trial are stated in Section 4.0.

10.4 Analysis Endpoints

Pharmacokinetic, safety, and efficacy endpoints that will be evaluated are listed below.

10.4.1 Efficacy/Immunogenicity/Pharmacokinetics Endpoints

10.4.1.1 Pharmacokinetic Endpoints

An initial description of PK endpoints is provided in Section 5.4.2.4. AUC_{0-24} , C_{max} , C_{trough} , and CL/F of EBR and GZR obtained by non-compartmental analysis (NCA) using intensive PK samples at Week 4 are the primary PK endpoints. The meal and soft food vehicle information may be considered in the PK analyses.

10.4.1.2 Efficacy Endpoints

An initial description of efficacy measures is provided in Section 5.4.2.1. The key efficacy endpoint is SVR_{12} , (HCV RNA $< LLOQ$, either TD[u] or TND, 12 weeks after the end of all study therapy).

An additional efficacy endpoint is SVR_{24} (HCV RNA $< LLOQ$, either TD[u] or TND, 24 weeks after the end of all study therapy).

10.4.2 Safety Endpoints

An initial description of safety measures is provided in Section 5.4.2.3 and ECIs are defined in Section 9.3.7. For this protocol, the proportion of participants who experience AEs of elevated laboratory values reported as ECIs (as described in Section 9.3.7) during the study therapy period will be estimated.

The proportions of participants with AEs of the following types at any time during the study therapy period will also be summarized: 1) with at least 1 AE; 2) with at least 1 drug-related AE; 3) with at least one SAE; 4) with at least 1 serious and drug-related AE; and 5) who discontinue due to an AE.

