9.3.7 Events of Clinical Interest (ECI)

Selected non-serious and serious adverse events are also known as Events of Clinical Interest (ECI) and must be reported to the Sponsor.

Events of clinical interest for this trial include:

1. an overdose of Sponsor's product, as defined in Section 9.4 – Treatment of Overdose, that is not associated with clinical symptoms or abnormal laboratory results.
2. first instance of ALT or AST >500 IU/L after initiation of study therapy through 14 days following treatment.*
3. first instance of ALT or AST >3x nadir AND >100 IU/L after initiation of study therapy through 14 days following treatment.*

*Note: The purpose of the criteria is to specify a threshold of abnormal hepatic tests that may require and additional evaluation for an underlying etiology. The trial site guidance for assessment and the follow up of these criteria can be found in the Investigator Trial File Binders (or equivalent).

Reporting requirements for ECIs are presented in [Table 8](#). Any ECI involving overdose or ALT/AST criteria are to be reported to the Sponsor within 24 hours.

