10.6.4 Statistical Methods for Safety Analyses

Safety results will be presented by Age Cohorts (12 to <18 years, 7 to <12 years, 3 to <7 years). Results of participants in the Expanded Cohorts will be reported separately from those in the Mini Cohorts, unless the same dose was given to both Mini and Expanded Cohorts within the age group.

Safety and tolerability will be assessed by clinical review of all relevant parameters, including AEs and laboratory parameters.

The analysis of safety parameters will follow a tiered approach ([Table 11](#)). The tiers differ with respect to the analyses that will be performed.

The first tier includes (1) AEs of elevated laboratory values that are reported as ECIs described in Section 9.3.7; (2) any AE; (2) a drug-related AE; (4) an SAE; (5) a serious and drug-related AE; and (6) an AE leading to discontinuation. Point estimates and 95% CIs will be provided for the proportion of participants with first tier AEs. The 95% CIs for the safety parameters will be estimated using the Clopper-Pearson method [Clopper, C. J. and Pearson, E. S 1934].

The second tier includes specific AEs by system organ class, vital signs, and standard laboratory safety tests at time points specified in the SoA. Point estimates will be provided for the proportion of participants with second tier AEs.

Missing safety laboratory or vital signs will be handled using the Data As Observed approach, that is, any missing value will be excluded from the analysis. The only exception is when a Baseline/Day 1 result is missing, this will be replaced with the latest pre-treatment result, if available.

The primary safety analysis will summarize the safety data for participants during the treatment period plus 14 days of follow-up.

Table 11 Analysis Strategy for Safety Parameters

Safety Endpoint	95% CI	Descriptive Statistics
AEs of elevated laboratory values that are reported as ECIs	X	X
Any AE	X	X
Any Serious AE	X	X
Any Drug-Related AE	X	X
Any Serious and Drug-Related AE	X	X
Discontinuation due to AE	X	X
Specific AEs or SOCs or PDLCs		X
Change from Baseline Results (laboratory vital signs)		X

95% confidence intervals will be calculated using the Clopper-Pearson method.
Note: AE = adverse event; CI = confidence interval; ECI = event of clinical interest; PDLC = pre-defined limits of change; SOC = System Organ Class; X = results will be posted.

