12.2 Appendix 2: Clinical Laboratory Tests

- Laboratory tests to be performed in this study are specified in [Table 15](#) and will be conducted by the central laboratory. The total amount of blood/tissue to be drawn/collected over the course of the study (from pre-study to post-study visits), including approximate blood/tissue volumes drawn/collected by visit and by sample type per participant can be found in [Table 16](#).

Table 15 Protocol-Required Safety Laboratory Assessments

Hematology	Chemistry	Urinalysis	Other
Hematocrit	Albumin	Blood	Coagulation Panel –PT –INR
Hemoglobin	ALP	Glucose	Choriogonadotropin beta (urine pregnancy test kits to sites)
Platelet count	ALT	Protein	Serum human chorionic gonadotropin (reflex when urine pregnancy test is “positive”)
RBC	AST	Specific gravity	HCV, Genotype
WBC	Bicarbonate	Microscopic exam (if abnormal results are noted)	HCV, Viral Load RNA (quantitative)
WBC Differential (result in % and Abs) –Basophils –Eosinophils –Lymphocytes –Monocytes –Neutrophils (Total)	Calcium	Bilirubin	FibroScan®
	Chloride	Ketones	
	Creatinine	Leukocyte esterase	Hepatitis B Serology Panel –HBsAg (perform at screening in all participants) –Anti-HBc, Total (screening only)
	Creatinine clearance (eGFR estimated by MDRD–NKDEP) (screening only)	Nitrite	HIV Serology Panel –HIV, Types 1 & 2 –HIV, Types 1 & 2 Confirmation by Inno-Lia HIV score–
	CPK	pH	(

Hematology	Chemistry	Urinalysis	Other
	GGT	WBC	
	Amylase	Bacteria	
	Lipase	Squamous epithelial cells	
	Glucose	RBC	
	Phosphorus		
	Potassium		
	Sodium		
	Total bilirubin		
	Direct bilirubin (if total bilirubin is elevated above the ULN)		
	Total protein		
	Blood urea nitrogen		

ALP=alkaline phosphatase; ALT=alanine aminotransferase; Anti-HBc=hepatitis B core antibody; Anti-HBs=hepatitis B surface antibody; AST=aspartate aminotransferase; CPK=creatine phosphokinase; eGFR=estimated glomerular filtration rate; GGT=gamma-glutamyl transpeptidase; HBsAg=hepatitis B surface antigen; HCV=hepatitis C virus; HIV=human immunodeficiency virus; INR=international normalized ratio; MDRD-NKDEP=Modification of Diet in Renal Disease–National Kidney Disease Education Program; PT=prothrombin time; RBC=red blood cell; RNA=ribonucleic acid; ULN=upper limit of normal; WBC=white blood cell.

Abbreviated blood chemistry includes only ALT, AST, ALP, total bilirubin, albumin, GGT, and CPK

Table 16 Approximate Blood Volumes Collected

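### The first-tier liver endpoint counts ALT/AST elevations only where they are reported as ECIs, and is neither derived from nor reconciled with the recorded laboratory values

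*Combined protocol and SAP*

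**What the plan says.** - **Endpoint.** Section 10.4.2 will estimate "the proportion of participants who experience AEs of elevated laboratory values reported as ECIs". The first tier in Section 10.6.4 repeats it as "AEs of elevated laboratory values that are reported as ECIs described in Section 9.3.7", with a point estimate and a Clopper-Pearson 95% interval.
- **Criteria.** Section 9.3.7 lists two liver-related ECIs: "first instance of ALT or AST >500 IU/L after initiation of study therapy through 14 days following treatment", and "first instance of ALT or AST >3x nadir AND >100 IU/L after initiation of study therapy through 14 days following treatment". Both are numeric.
- **Reporting duty.** Section 9.3.7 adds: "Any ECI involving overdose or ALT/AST criteria are to be reported to the Sponsor within 24 hours".
- **Data.** Appendix 2 says that the laboratory tests "will be conducted by the central laboratory". ALT and AST are in the complete panel and also in the short one: "Abbreviated blood chemistry includes only ALT, AST, ALP, total bilirubin, albumin, GGT, and CPK". Table 16 shows one panel or the other at screening, Day 1, every treatment visit, FW4, FW12 and FW24.
- **Other laboratory summaries.** The second tier in Section 10.6.4 covers standard laboratory tests. Table 11 lists pre-defined limits of change (PDLC) and change from baseline, both with descriptive statistics and no confidence interval. The PDLC limits are not given.
- **Window.** Section 10.4.2 counts events in the study therapy period. Sections 9.3.7 and 10.6.4 both run to 14 days after treatment.

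No section says that ECIs will be derived from the laboratory data or checked against them.

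**The concern.** Section 3.3 names ALT elevation as the safety signal linked to higher GZR exposure, and Section 3.2.3.2 places the elevations around Weeks 8 to 10. The one liver summary with an interval depends on two acts at the site: recognising that a value meets a criterion, and reporting it.

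The second criterion is the harder one to spot. It needs the lowest value so far for each child, and it can be met by a value below baseline. That differs from the plan's general approach to adverse events: Section 9.5 looks for clinically significant changes from the pre-treatment assessments, and Section 9.5.6 sets aside findings associated with the underlying disease unless they are worse than expected. Table 4 admits children with ALT up to 10 times ULN, so large falls on treatment followed by partial rises are possible. Table 8 describes post-allocation ECI reporting by reference to potential drug-induced liver injury and does not repeat the numeric thresholds.

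In cohorts of this size, a single unreported participant changes the published rate visibly and can turn one case into none.

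**Working it through.** **1. The plan's own figures.** Inputs from Section 10.9.3 and Table 14: N = 22, two-sided 95% Clopper-Pearson.

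- Chance of at least one event at 1% incidence: 1 − 0.99^22 = 0.198, against the stated 20%.
- Upper limit for x of n: the 0.975 quantile of Beta(x+1, n−x). For 0/22 this is 1 − 0.025^(1/22) = 15.4%.
- All 14 rows of Table 14 reproduce to the printed decimal.

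**2. Effect of one missed participant.** Same formula, with the count reduced by one:

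| N | True count: estimate (upper limit) | Reported count: estimate (upper limit) |
|---|---|---|
| 22 | 2: 9.1% (29.2%) | 1: 4.5% (22.8%) |
| 22 | 1: 4.5% (22.8%) | 0: 0% (15.4%) |
| 15 | 1: 6.7% (31.9%) | 0: 0% (21.8%) |
| 12 | 1: 8.3% (38.5%) | 0: 0% (26.5%) |
| 7 | 1: 14.3% (57.9%) | 0: 0% (41.0%) |

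N = 7 is a Mini Age Cohort (Table 2). Section 10.6.4 reports it separately when its dose differs from that of the Expanded Cohort.

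**3. How often cases would occur with none reported.** The documents give no incidence for these criteria and no reporting completeness, so both are assumed. Let p be the true incidence and s the chance that a case is reported, independently between participants. Then

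P(at least one case, none reported) = (1 − ps)^22 − (1 − p)^22.

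For p = 5% and s = 90%: 0.955^22 − 0.95^22 = 4.0%.

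| s (p = 5%, N = 22) | At least one reported | Cases occur, none reported |
|---|---|---|
| 100% | 67.6% | 0% |
| 90% | 63.7% | 4.0% |
| 80% | 59.3% | 8.4% |
| 70% | 54.3% | 13.3% |
| 50% | 42.7% | 24.9% |

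Over s = 90% to 50%, the last column runs from 1.8% to 9.4% if p = 1%, and from 2.7% to 22.5% if p = 10%.

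In these under-reporting scenarios (p = 1%, 5% or 10%), the interval from the reported count still contains the true incidence 98.3% to 99.9% of the time, because it is so wide. The harm is to the estimate, to the upper limit, and to whether any case is shown at all.

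**4. Whether the other laboratory rows fill the gap.** Take assumed ALT values of 200 IU/L at baseline, 30 at nadir and 120 at Week 8. The ratio to nadir is 120/30 = 4, and 120 exceeds 100, so the second criterion is met. Change from baseline is 120 − 200 = −80 IU/L, which reads as improvement. A PDLC row would show this case only if its limits included a rise from nadir, and the plan does not state those limits.

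**The case against.** The strongest reply is that the definition is already objective. The thresholds are numbers and reporting is due within 24 hours, so an unreported crossing is a deviation, not a matter of judgement. There are safeguards too. Investigators must review each laboratory report (Section 9.5.6). The sponsor checks data quality and monitors verify source data (Appendix 3). The eDMC reviews safety about every six months (Section 10.7). The discontinuation and enrollment-pause rules (Sections 8.1 and 5.4.2.3.2) make sites follow ALT and AST anyway. The ECI proportion is one of six first-tier rows, and no pause or sample-size decision rests on it.

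Most of this stands, and it lowers the chance of a miss. It does not make the endpoint value-based. The overlap with the discontinuation and pause rules is also partial: apart from the limit of 500 IU/L, those ALT/AST rules add a bilirubin or INR condition to the rise from baseline or nadir, so a rise from nadir alone falls outside them.

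Three stronger readings are not supported:

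- A reader might infer that the whole liver analysis rests on investigator reports. It does not: Table 11 plans PDLC and change-from-baseline summaries of the measured values.
- A reader might infer that central-laboratory data would give a complete count. They would not. After Week 12 the next scheduled chemistry is FW4, with a window of two weeks either side, so little of the 14-day post-treatment period has a scheduled draw. Section 10.6.4 excludes missing values, and Section 9.5.6 allows local results to be recorded. A central-only count could lose a crossing seen locally.
- A reader might infer that under-reporting is known or likely to be large. The documents give no figure, so every completeness value above is an assumption.

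**Conclusion.** The point holds for the first-tier row. The only ALT/AST-specific proportion with an interval is defined by what is reported, although its criteria can be computed from values already collected, and nothing in the plan ties the two together. The second-tier laboratory summaries do not replace it: their limits are unstated and not linked to Section 9.3.7, they carry no interval, and change from baseline can miss a rise from nadir.

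The effect is one participant at a time: at N = 22, 4.5 percentage points on the estimate and about 6 to 7 points on the upper limit (29.2 − 22.8 = 6.4; 22.8 − 15.4 = 7.4). The 4% to 25% chance of showing no cases when some occurred rests on an assumed 5% incidence, assumed completeness of 90% to 50%, and independent reporting. No sample size, alpha level or stated precision figure changes. The difference in window between Section 10.4.2 and Sections 9.3.7 and 10.6.4 is a separate inconsistency in the same endpoint.

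**What to change.** 1. In Sections 10.4.2 and 10.6.4 and Table 11, add a derived endpoint: the proportion of participants meeting either Section 9.3.7 ALT/AST criterion, computed from all recorded values (central, plus any local results captured), from first dose through 14 days after treatment, with a Clopper-Pearson 95% interval. Write down how nadir is computed, since Section 9.3.7 does not define it.
2. Keep the reported-ECI proportion and present it beside the derived one.
3. Reconcile the two participant by participant before database lock, and list any remaining differences with reasons.
4. Align the analysis window in Section 10.4.2 with Sections 9.3.7 and 10.6.4.
5. State the PDLC limits for ALT and AST, or say where they are held.

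No visit, sample or clinical rule changes. The cost is a little programming and a reconciliation listing. The limitation to state with the result is that the post-treatment part of the window has few scheduled draws.
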